Degree	Institute	University/Board	Field	Year
M.B.B.S			Passed	

3. Field of study : Nephrology
4. Research experience : None
5. Percentage of time to be devoted to this project : 100%
6. Number of Scientific Publication : None

.....

Signature of the Student

PART-C

Summary

Background: Pruritus is a common and distressing symptom among hemodialysis patients with chronic kidney disease (CKD), significantly impacting their quality of life. Difelikefalin, a selective kappa-opioid receptor agonist, has shown promise in alleviating CKD associated pruritus (CKDaP). However, its efficacy and safety in the Bangladeshi population remain under-explored. **Objectives:** This study aims to evaluate the effect of Difelikefalin, compared to placebo, in reducing pruritus, improving quality of life in CKD patients on maintenance hemodialysis. **Materials and Methods:** A randomized, placebo-controlled trial, double-blinded, will be conducted in the Department of Nephrology of Chittagong Medical College Hospital, Chattogram, Bangladesh for one and half years. A total of one hundred two CKD patients on maintenance hemodialysis will be included in this study. Patient with moderate-to-severe pruritus (Worst Itching Intensity Numerical Rating Scale [WI-NRS] score ≥ 4) will be enrolled and randomly assigned in a 1:1 ratio to receive either Difelikefalin (0.5 mcg/kg) or a placebo intravenously after each hemodialysis for 6 weeks. The primary outcome measure will be the change in WI-NRS score from baseline to week 6. Secondary outcomes will be measured by Skindex 10 scale. Adverse events and safety measures will also be recorded. The primary analysis will follow either an intention-to-treat or a per-protocol approach and will be performed using SPSS version 27. **Discussion:** Data from previous studies indicate that Difelikefalin can reduce the severity of itching and improve the quality of life in CKD patients on maintenance hemodialysis. Clinical trials are needed to better understand the safety and efficacy of Difelikefalin in CKD patients in our population.

PART-D

1. Introduction:

Chronic kidney disease-associated pruritus (CKD-aP), alternatively termed Uremic pruritus (UP), represents a frequent, distressing, and often incapacitating clinical manifestation among individuals diagnosed with chronic kidney disease (CKD) or end-stage renal disease (ESRD) (Elhag et al., 2022; Elsayed et al., 2023). Characterized by persistent, intense itching—typically generalized but occasionally localized—CKD-aP disproportionately affects patients undergoing hemodialysis, with epidemiological studies reporting a strikingly variable prevalence ranging from 22% to 84% in this population. Notably, a substantial subset of these patients, approximately 20–40%, endure moderate-to-severe pruritus, which profoundly diminishes their quality of life (Daraghmeah et al., 2022; Rehman et al., 2018).

The ramifications of CKD-aP extend far beyond superficial discomfort. The condition is intricately linked to a constellation of physical and psychological burdens, including chronic sleep disturbances such as insomnia, relentless fatigue, and dermatological complications arising from repetitive scratching, such as excoriations, lichenification, and secondary infections (Lu et al., 2021; Lu et al., 2022). Psychosocially, patients frequently grapple with emotional distress, including feelings of embarrassment, social withdrawal, and stigmatization due to visible skin lesions, which may exacerbate preexisting mental health challenges like anxiety, depression, and irritability. Furthermore, emerging evidence underscores a concerning association between CKD-aP and elevated mortality risks; dialysis-dependent patients with CKD-aP exhibit higher rates of all-cause mortality, as well as increased fatalities linked to cardiovascular events and systemic infections, suggesting a potential interplay between chronic inflammation, immune dysregulation, and disease progression (Grochulska et al., 2019; Sukul et al., 2021). There is, therefore, a need for effective interventions for the treatment of CKD-aP. Off-label treatments may include antihistamines, topical corticosteroids, and gabapentin or pregabalin; although there are reports that treatments like gabapentin and pregabalin are effective at reducing itch, their side effects sometimes prevent their use in this patient population (Hercz et al., 2020; Skrzypczak et al., 2024).

The pathogenesis of CKD-aP is incompletely understood. Several hypotheses have been proposed, including metabolic disturbances, dysregulated immune response, and imbalances in the endogenous opioid system, with peripherally distributed kappa opioid receptors potentially playing a role (Brennan 2024; Skrzypczak et al., 2024).

Difelikefalin is a peripherally restricted, selective kappa opioid receptor agonist that exerts antipruritic effects by means of activation of kappa opioid receptors on peripheral neurons and immune cells (Gardell, et al., 2008). The hydrophilic small-peptide structure restricts passive diffusion across membranes, thereby limiting access to kappa opioid receptors in the central nervous system (O'Connor et al., 2010).

European Medicines Agency (EMA) and Federal Drug Administration (FDA) approved difelikefalin, the first drug specifically indicated for CKD-aP in dialyzed patients, which demonstrated efficacy in two Phase 3 clinical trials (Topf et al., 2022). The development of this targeted medication, supported by solid evidence of its effectiveness and safety, increased awareness and understanding of this condition (Buades et al., 2024). According to the most current expert recommendations, difelikefalin should be first-line medication for patients with moderate-to-severe CKD-aP undergoing dialysis (Agarwal et al., 2022; Skrzypczak et al., 2024).¹³ Other therapies should only be considered as first-line choice for those patients only if difelikefalin is not available (Agarwal et al., 2022; Skrzypczak et al., 2024).

Although difelikefalin showed promise as a treatment for CKD-aP in dialyzed patients, particularly through its selective κ -opioid receptor agonist activity, the current body of evidence has limitations. Approximately 20% of patients did not report clinically meaningful reductions in itch intensity, 30% did not present clinically relevant improvements in QoL (Weiner et al., 2022). Several studies, including the pivotal KALM-1 and KALM-2 trials, demonstrated significant efficacy in reducing itch intensity and improving quality of life in hemodialysis patients (Topf et al., 2022).

Difelikefalin's safety varies according to dose. Regarding safety, the majority of research revealed that adverse effects increased in frequency in a way that was dose dependent. Across all trials, nausea, vomiting, dizziness, diarrhea, and disturbances in gait were the most frequently reported adverse events (Enggalhardjo, et al., 2024). A dosage of 0.5 µg/kg of difelikefalin proved to have the most favorable benefit-risk profile, and it was safe to use up to 1.0 µg/kg (Narita et al., 2022).

Though difelikefalin appears to be a promising agent for the management of CKD-aP, evidence is still under-powered due to the paucity of the current data; therefore, more robust randomized controlled trials (RCTs) are required to confirm the benefit of difelikefalin (Saeed et al., 2024).

While recent clinical trials in Western populations have demonstrated its efficacy, data from low- and middle-income countries, such as Bangladesh, are scarce. The prevalence of CKD in Bangladesh surpasses the global and even South Asian averages. About 20 million people are suffering from chronic kidney disease, and of them, approximately 35,000–40,000 develop ESRD each year (Mostafi and Jabin 2023). This trial aims to evaluate the superiority of Difelikefalin over placebo in reducing pruritus severity among hemodialysis patients in a tertiary-level teaching hospital in Bangladesh.

2. Rationale

Pruritus in hemodialysis patients is a chronic and highly irritating condition associated with chronic kidney disease (CKD) that adversely affects sleep, mood, social participation and overall quality of life. The commonly used agents for CKD-associated pruritus often have limited efficacy or tolerability in many patients. Oral medications used to manage this condition are frequently associated with poor compliance due to a high pill burden. On the other hand, intravenous administration of difelikefalin after hemodialysis offers a practical and patient-friendly alternative. It uses the same dialysis access, avoiding the need for extra needle insertions. Previous studies have demonstrated that difelikefalin improves outcomes in patients with CKD-associated pruritus and enhances their quality of life. To my extensive search, data regarding the use of difelikefalin for CKD-associated pruritus in our population is scarce. This study aims to explore the effect of difelikefalin on CKD-associated pruritus in maintenance hemodialysis (MHD) patients in our population.

3.1. Research questions:

- What is the effect of difelikefalin on CKD-associated pruritus in patients on maintenance hemodialysis?

3.2 Research hypothesis:

- Difelikefalin effectively reduces CKD–associated pruritus in maintenance hemodialysis patients.

4. Objectives

4.1 General objective:

- To evaluate the effect of difelikefalin in CKD-associated pruritus on maintenance hemodialysis patients.

4.2 Specific objectives:

- I. To determine the baseline scores of the WINRS scale and Skindex-10 scale in CKD-associated pruritus on maintenance hemodialysis patients..
- II. To estimate and compare the changes in the WINRS scale, and Skindex-10 Scale between the experimental and control groups.
- III. To assess the tolerability and detect any adverse effect of Difelikefalin in patients with CKD-associated pruritus on maintenance hemodialysis throughout the study period.

5. Materials and method:

5.1. Type of study: Randomized, placebo-controlled, double-blinded trial,

5.2 Place of Study: Department of Nephrology, Chittagong Medical College Hospital, Chattogram, Bangladesh.

5.3 Study period: One and half years from acceptance of protocol.

5.4 Study population: Adult CKD stage-5 patients on MHD in the dialysis unit of the Department of Nephrology, CMCH during the study period.

5.5 Study groups: Based on the interventions, there will be two groups in the study

I. Experimental group:

Standard symptomatic treatment for itching + Intravenous difelikefalin

II. Control group:

Standard symptomatic treatment for itching + Placebo

5.6 Sampling technique: Consecutive sampling. From the Selected participants, the intervention and control will be randomly assigned in a 1:1 ratio (block size of four) through computer-generated randomization.

5.7. Inclusion criteria:

- i. Adults aged ≥ 18 years.
- ii. Patient with chronic kidney disease on HD for ≥ 3 months.
- iii. Moderate-to-severe pruritus (WI-NRS score ≥ 4).
- iv. Able to communicate clearly with the Investigator .
- v. Willing and able to provide written informed consent prior to participating in this study.

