5.8 Exclusion criteria

- i. Known case of Primary skin disease associated with Itching.
- ii. Known case of liver disease.
- iii. Known case of iron deficiency anaemia ,hematological malignancy.
- iv. Known case of hypothyroidism & hyperthyroidism.
- v. Known case of allergic reaction to Opiates .
- vi. Pregnancy.
- vii. Drug abuse, or substance dependence.

5.9. Sample size: Sample size calculation for hypothesis testing of difference between two proportions:

$$n = \frac{p(100 - p) + q(100 - q)}{(p - q)^2} (z_{\alpha} + z_{\beta})^2$$

Where,

Z_{α} = Z value of standard normal distribution at a definite level of significance

Z_{β} = Z value of standard normal distribution at a definite level of power

p = Proportion of patients with expected outcome (response rate) in the experimental group

q = Proportion of patients with expected outcome (response rate) in the control group

Here,

Z_{α} = 1.96 at 95% Confidence Interval

Z_{β} = 1.63 at 95 % power

p = 64% (Fishbane et al., 2020b)

q = 29% (Fishbane et al., 2020b)

So,

$$n = \frac{64(100.0 - 64) + 29(100.0 - 29)}{(64 - 29)^2} (1.96 + 1.63)^2 \approx 46$$

Considering 10% lost to follow-up final sample will be

$$(46 + 46 \times 10\%) \approx 50.6 \approx 51$$

That means 51 patients in each group will be needed in each group to test the hypothesis.

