5.10. List of variables

Variables	Type	Value	Expression
Clinical			
Age	Discrete	In completed years	Mean±SD
Sex	Categorical	Male/Female	Frequency (%)
Duration of HD	Discrete	In completed years	Mean±SD
Duration of pruritus	Discrete	In completed months	Mean±SD
Cause of CKD	Categorical	GN/HTN/DM	Frequency (%)
Baseline use of antipruritic medication	Categorical	Absent/Present	Frequency (%)
WI-NRS score	Discrete	0-10	Mean±SD
Skindex-10 scale total score	Discrete	0-60	Mean±SD
Biochemical			
Calcium	Continuous	mmol/l	Mean±SD
Phosphate	Continuous	mmol/l	Mean±SD
PTH	Continuous	pg/ml	Mean±SD

Operational definitions:

- **Chronic Kidney Disease-Associated Pruritus:** CKD-aPis defined as severe and persistent itching directly related to kidney disease, without other underlying skin or systemic causes to explain the itching. (Hector alve..et al 2020)
- **MHD:** Maintenance haemodialysis was defined as regular haemodialysis treatment for at least 3 months for the management of ESKD.(Mambap, A.T., Che, I.A., Mahamat, M. *et al.* 2022)
- **Skindex-10:** The Skindex-10 scale was developed specifically for uremic pruritus and measures the weekly effect of itch across three domains (disease, mood and emotional distress, and social functioning) Scores on the Skindex-10 scale range from 0 to 60, with higher scores indicating worse itch-related quality of life. (Mathur et al., 2010).
- **Moderate-to-severe pruritus** will be defined as a mean score of >4 points on the 24-hour WI-NRS score calculated.Itching severity scores have been categorized in the literature as mild (<4), moderate (≥ 4 to <7), or severe (≥ 7) (Reich et al., 2012).
- **Efficacy outcomes:** The primary efficacy outcome will be the percentage of patients who will have an improvement (decrease) of at least 3 points from baseline at week 6 in the weekly mean score on the daily WI-NRS (Fishbane et al., 2020). The prespecified secondary efficacy outcomes will be the mean change from baseline at week 6 in the Skindex-10 scale total score (Fishbane et al., 2020).
- **Standard Symptomatic Treatment for Itching:** Standard Symptomatic treatment using antihistamin is useful. Gabapentin or Pregabalin UVB therapy ,oral charcoal or nalfuralfine might be the next line of therapy.(Mettang and kremer 2014)

5.11. Data collection instrument: A structured pretested case record form.

5.12. Data collection procedure:

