Safety will be evaluated by monitoring adverse events, vital signs, clinical laboratory measurements in both group.

5.13. Data analysis:

Data will be entered into an Excel sheet to generate the master sheet. After completion of data collection, master sheet will be fed into SPSS (Windows version 27.0) for analysis. This study has two types of data: Categorical and quantitative data. Kolmogorov–Smirnov (K-S) test will be used to determine the data distribution. Finding if there is a significant difference between the data, independent samples t-test (or Mann–Whitney test in case of non-parametric data) and Chi-square test for continuous and categorical data, respectively will be used. The difference between the repeated variable in distinct visits using repeated ANOVA with the change from baseline in the weekly mean WI-NRS scale, Skindex 10 Scale. The adjusted mean difference between the groups and its two-sided 95% CI will be presented. A p -value < 0.05 will be considered significance.

5.14. Expected outcomes: Difelikefalin will significantly reduce pruritus severity compared to placebo. Participants receiving difelikefalin will report improvements in quality of life and will exhibit a favorable safety profile, with no major adverse events.

5.15. The utilization of results: This trial will provide critical evidence on the effectiveness and safety of difelikefalin in a resource-limited setting, addressing a significant unmet need in the management of CKD-aP. If proven effective, difelikefalin could become a standard treatment option for CKDaP and improve the quality of life for hemodialysis patients in Bangladesh and similar populations globally. Efforts will also be made to present these results at conferences and publish them in peer-reviewed national and international journals. The results and observations of the study will be published as a thesis and submitted to the respective university as a part of the requirement for the MD (Nephrology) Phase B examination purpose. The results of the study will be presented to the Department of Nephrology, CMCH.

[figure not shown]

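### The Summary and section 5.10 name two different primary outcomes, and nothing says which one decides superiority

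*Protocol*

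**What the plan says.** Two places in the protocol use the word primary for an outcome, and they disagree.

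- **Part C, Summary:** "The primary outcome measure will be the change in WI-NRS score from baseline to week 6". No responder threshold is mentioned.
- **Section 5.10, operational definitions, efficacy outcomes:** "The primary efficacy outcome will be the percentage of patients who will have an improvement (decrease) of at least 3 points from baseline", assessed at week 6 on the weekly mean of the daily WI-NRS. The only secondary efficacy outcome listed there is mean change in the Skindex-10 total score.

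The other relevant sections name no primary:

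- **Section 4.2, objective II:** "To estimate and compare the changes in the WINRS scale, and Skindex-10 Scale between the experimental and control groups".
- **Section 5.9:** "Sample size calculation for hypothesis testing of difference between two proportions", with response rates of 64% and 29%, giving 51 per group.
- **Section 5.13:** t-test or Mann-Whitney for continuous data, chi-square for categorical data, and repeated ANOVA on change from baseline in weekly mean WI-NRS and in Skindex-10. Then: "The adjusted mean difference between the groups and its two-sided 95% CI will be presented". One 0.05 threshold applies throughout.

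The end of the Introduction says the trial is meant to evaluate superiority over placebo in pruritus severity.

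**The concern.** A change in score and a responder percentage are different endpoints, with different tests and effect measures. Either can be significant when the other is not. A superiority trial has to say in advance which result establishes superiority, and this protocol gives two answers.

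Two things are at stake. If either result may be presented as the primary, the nominal 5% error rate no longer applies. And the trial is sized for one of the two outcomes, while the only model-based analysis and the only effect estimate it names are on the scale of the other.

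**Working it through.** **1. Which endpoint each section supports**

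| Section | Outcome it fits | Calls it primary? |
|---|---|---|
| Summary | Change in WI-NRS score | Yes |
| 5.10 efficacy outcomes | Responder, at least 3 points | Yes |
| 4.2 objective II | Changes in WI-NRS and Skindex-10 | No |
| 5.9 | Responder proportions | No |
| 5.13 repeated ANOVA, adjusted mean difference | Change scores (WI-NRS, Skindex-10) | No |
| 5.13 chi-square | Any categorical variable | No |

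The direct conflict is between the first two rows. The rest do not resolve it: 5.9 sides with 5.10, and the more specific analysis in 5.13 sides with the Summary.

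**2. The protocol's own sample size**

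Inputs from 5.9: p = 64, q = 29, z_α = "1.96 at 95% Confidence Interval", z_β = 1.63.

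- p(100 − p) + q(100 − q) = 64×36 + 29×71 = 2304 + 2059 = 4363
- (p − q)² = 35² = 1225
- (1.96 + 1.63)² = 12.888
- n = 4363 / 1225 × 12.888 = 45.90, rounded up to 46
- 46 × 1.10 = 50.6, rounded up to 51 per group, 102 in total

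The stated figure reproduces. It is a calculation for the responder outcome only. With a pooled two-proportion test, power at 64% versus 29% is about 93% with 46 evaluable per group and about 95% with 51.

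**3. The same N applied to a change score**

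The protocol gives no mean difference and no SD for WI-NRS change, so power cannot be derived from it. Over an assumed range of d = difference/SD, with 46 per group and power = Φ(d·√(46/2) − 1.96):

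| Assumed d | 0.4 | 0.5 | 0.6 | 0.75 |
|---|---|---|---|---|
| Power | 48% | 67% | 82% | 95% |

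**4. Type I error if either outcome could carry the claim**

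For two independent tests at 0.05: 1 − 0.95² = 9.75%. These two outcomes come from the same scores and are strongly correlated, so the true figure is lower. It was simulated with no treatment effect, normal change scores, complete data, a t-test on the change and an uncorrected two-proportion test on the responder rate, with 40,000 trials per setting. The assumed common responder rate was 29% (the control rate in 5.9) or 46.5% (the mean of 64% and 29%).

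| n per group | Responder rate | t-test alone | Responder test alone | Either |
|---|---|---|---|---|
| 46 | 29% | 4.9% | 4.9% | 8.0% |
| 46 | 46.5% | 5.0% | 4.6% | 7.5% |
| 51 | 29% | 4.9% | 5.0% | 8.0% |
| 51 | 46.5% | 5.0% | 5.9% | 8.4% |

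The correlation between the two test statistics was 0.75 to 0.80. In the last row part of the excess comes from the discreteness of the responder test, which alone rejects in 5.9% of trials.

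**The case against.** The strongest reply is that the Summary sentence is shorthand. It is one sentence in an abstract, while 5.10 is the operational definition and 5.9 is sized on it. On that reading the primary is the responder rate, and the repeated ANOVA and adjusted mean difference in 5.13 serve Skindex-10 change. Much of this stands. Only the Summary calls the change score primary. Objective II names no primary, and a responder rate is also a way to compare changes. The mean±SD entry for WI-NRS in the variable list is a display format for the raw score. A reader might infer that most of the protocol treats the primary as continuous, but the text does not go that far.

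The shorthand reading still does not remove the conflict. Section 5.13 applies the repeated ANOVA to WI-NRS change by name, 5.10 does not list WI-NRS change as secondary, and the Summary never mentions a responder rate. A separate statistical analysis plan could add detail to a primary outcome, but it would not remove two conflicting definitions from the protocol.

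Three other stronger readings are not supported:

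- **That the outcome will be picked after the data are seen.** The protocol leaves the choice open. It states no such intent and no either-outcome success rule.
- **That the error rate is higher still, once the intention-to-treat or per-protocol choice and the Mann-Whitney test are added.** The open analysis set is a separate matter, and 5.13 ties Mann-Whitney to the data distribution.
- **That the change score would be underpowered.** It has no stated justification, which is a different thing. If change scores were normal with equal SD, 64% versus 29% past one threshold would imply a difference of 0.358 + 0.553 = 0.91 SD, and about 99% power at 46 per group.

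The lack of a promised confidence interval for the responder rate is also not a defect in itself, since an analysis plan could supply it.

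**Conclusion.** The contradiction is real and needs correcting: two outcomes on different scales are both labelled primary, and nothing says which decides superiority. The stated N is arithmetically sound but belongs to the responder outcome.

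If either outcome at p<0.05 were allowed to carry the claim, the two-sided type I error would be about 7.5% to 8.4% instead of 5%. That range rests on assumed normal change scores, complete data and assumed responder rates, and it is conditional on a success rule that the protocol leaves possible but does not state.

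**What to change.** Before unblinding:

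- **Primary outcome.** Name the responder outcome as the single primary in every section that mentions one, in 5.10's full definition: a decrease from baseline of at least 3 points at week 6 in the weekly mean of the daily WI-NRS. A shortened version that drops the weekly mean would create a third definition. This choice follows the protocol, because 5.9 is sized on a response rate.
- **Summary.** Correct the primary outcome sentence to match.
- **Section 5.13.** State that the primary is tested by the chi-square test already named there, and reported as the difference in proportions with its 95% CI.
- **Secondary outcomes.** List change in WI-NRS in 5.10 alongside Skindex-10 change. The repeated ANOVA and adjusted mean difference then have a clear place.

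No testing hierarchy among the secondaries is needed to resolve the conflict, and objective II can stay as it is. The cost is wording only: N remains 51 per group. While aligning the text, check that the single WI-NRS entry per time point on the case record form can hold the weekly mean that 5.10 requires. That is a separate question from this one.

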Appendix
Case record form

Protocol Title: “Effect of Difelikefalin on CKD-Associated Pruritus in Patients on Maintenance Hemodialysis: A Randomized, Placebo-Controlled Trial”

Patient’s identification			
1	Patient ID No.		
2	Patient name :		
3	Adress		
4	Contact no:		
5	Study group	Experimental=1 Control=2	
Demographic characteristics			
1	Age:years	
2	Sex:	0=Female 1=Male	
Clinical characteristics			
1	Duration of HDMonths/years	
2	Duration of pruritusMonths/years	
3	Etiology of CKD	1=HTN 2=DM 3=GN 4=Others	
4	Baseline use of antipruritic medication	Anti histamin- Others-	
5	Online Kt/V		
Biochemical			
1	Calcium(mmol/l)		
2	Phosphate(mmol/l)		
3	PTH(pg/ml)		

	Follow-up data	Baseline	At 3-wk	At 6-wk
1	WI-NRS score			
2	Skindex-10 scale total score			

	Adverse Effect		3 weeks	6weeks
1	Nausea	N0= 0 Yes= 1		
2	Vomiting	N0= 0 Yes= 1		
3	Dizziness	N0= 0 Yes= 1		
4	Abdominal pain	N0= 0 Yes= 1		
5	Muscle spasm	N0= 0 Yes= 1		
6	Fall	N0= 0 Yes= 1		
7	Withdrawal	N0= 0 Yes= 1		
8	Expired	N0= 0 Yes= 1		
9	Others	N0= 0 Yes= 1		

	Complete the study per the Protocol 0= No 1= yes
	If not reason for drop-out 1. Adverse experience 2. Failure to return for follow-up 3. Patients refuse treatment 4. Patient died 5. Non-co-operation 6. Insufficient therapeutic response

Signature of the researcher:

Signature of the Guide/Co-guide

A. Worst Itching Intensity Numerical Rating Scale

INSTRUCTIONS

Please indicate the intensity of the **WORST ITCHING** you experienced over the past 24 hours by marking the box with the number that best describes it. After completing the scale below, please provide your initials in the **SUBJECT INITIALS** box indicating that you completed the scale by yourself and the **DATE** and **TIME** you completed the scale.

Worst Itching Over the Past 24 Hours

Please indicate the intensity of the **WORST ITCHING** you experienced over the past 24 hours.

0	1	2	3	4	5	6	7	8	9	10
										
NO ITCHING					WORST ITCHING IMAGINABLE					

B. Skindex-10 Scale

INSTRUCTIONS: During the past WEEK , how often have you been bothered by:							
	0 (Never bothered)	1	2	3	4	5	6 (Always bothered)

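### The Summary allows either intention-to-treat or per-protocol as the primary analysis of a superiority trial, and nothing else in the protocol settles which

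*Protocol*

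**What the plan says.** Part C, Summary: "The primary analysis will follow either an intention-to-treat or a per-protocol approach". No rule or time for choosing is given.

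Section 5.13 (Data analysis) starts with "After completion of data collection, master sheet will be fed into SPSS (Windows version 27.0) for analysis" and goes on to list tests. It names no analysis set and does not say how drop-outs are handled. No section defines a per-protocol set. The Introduction gives the aim as superiority over placebo.

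The case record form in the Appendix has a completion item, "Complete the study per the Protocol 0= No 1= yes", followed by "If not reason for drop-out 1. Adverse experience" and five further reasons, the last two being "5. Non-co-operation 6. Insufficient therapeutic response". Section 5.9 allows for attrition once, for both arms together: "Considering 10% lost to follow-up final sample will be" 51 per group.

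The primary endpoint is described in two ways. The Summary gives the change in WI-NRS score from baseline to week 6. The operational definitions under 5.10 give the percentage of patients with an "improvement (decrease) of at least 3 points from baseline at week 6 in the weekly mean score on the daily WI-NRS".

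**The concern.** A protocol can leave the analysis set to a later plan. This one takes a position, and the position is two alternatives with no way to decide between them. In a superiority trial they are not interchangeable: the all-randomised comparison keeps the protection of randomisation, while a per-protocol comparison conditions on what happened afterwards.

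Two things are at stake. If the choice can be made with results in hand, there are two chances at significance. If per-protocol is chosen, the likely basis for the set is the form's completion item, which is the form's only completion status. Some of its reasons for non-completion, such as adverse experience and "6. Insufficient therapeutic response", are related to tolerability or outcome, so removing those patients can bias the estimate.

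**Working it through.** **Inputs from section 5.9:** response 64% v 29%, z values 1.96 and 1.63, 10% loss, 51 per arm. **Assumptions:** the split of drop-out by arm, and every drop-out being a non-responder. All figures are for the responder endpoint.

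**Step 1: reproduce the plan's sample size.** (0.64×0.36 + 0.29×0.71)/(0.35)² × (1.96+1.63)² = 45.9, so 46. Then 46 × 1.10 = 50.6, so 51. Both figures agree with 5.9.

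**Step 2: type I error if either set may be claimed.** Simulation with 51 per arm, 29% response among all randomised in both arms, drop-outs drawn from the non-responders, and a pooled z-test at two-sided 5%.

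| Drop-out, drug / placebo | All randomised | Per-protocol | Either, two-sided | Either, favouring drug |
|---|---|---|---|---|
| 10% / 10% | 5.0% | 5.0% | 6.1% | 3.0% |
| 15% / 5% | 5.1% | 6.7% | 8.3% | 5.7% |
| 5% / 15% | 5.2% | 6.7% | 8.3% | 2.6% |

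The nominal value in the last column is 2.5%. If 29% is instead set as the rate among completers, the two-sided either-set figures are 6.0% at 10%/10% and 7.9% at 15%/5%. Under that set-up the 15%/5% case is not a strict null for the all-randomised test, because counting drop-outs as failures gives 0.29×0.85 = 24.7% v 0.29×0.95 = 27.6%. The two set-ups agree on about 6% and about 8%.

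**Step 3: direction of the per-protocol bias.**

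*If 64% v 29% holds among all randomised* (difference 35.0 points), the per-protocol rate in an arm is the all-randomised rate divided by (1 − drop-out):
- 10%/10%: 0.64/0.90 − 0.29/0.90 = 38.9 points
- 15%/5%: 0.64/0.85 − 0.29/0.95 = 44.8 points
- 5%/15%: 0.64/0.95 − 0.29/0.85 = 33.3 points

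*If 64% v 29% holds among completers* (per-protocol difference 35.0 points), the all-randomised rate is the completer rate times (1 − drop-out):
- 10%/10%: 0.576 − 0.261 = 31.5 points
- 15%/5%: 0.544 − 0.2755 = 26.9 points
- 5%/15%: 0.608 − 0.2465 = 36.2 points

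On either reading, per-protocol overstates the difference in the first two patterns and understates it in the third.

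**Step 4: power.** Exact power of the Pearson chi-square test is 91.7% for all randomised (51 per arm, 57.6% v 26.1%) and 92.8% for completers only (46 per arm, 64% v 29%). The difference is 1.1 points.

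**The case against.** The strongest reply is that the Summary is not the analysis section, and that a statistical analysis plan, if there is one, may name a single set before unblinding. If that happened, there would be no type I error inflation. This is a fair limit: the figures in Step 2 are what an unrestricted choice costs, not a prediction. But nothing in the protocol says the choice will be made before the data are seen, and the sentence offers both sets as primary.

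Three stronger readings are tempting, and the document does not support them.

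- A reader might infer that the case record form removes treatment failures and patients who stop for adverse events. It does not. It records completion and a reason, which an intention-to-treat analysis needs as well, and no passage links that item to an analysis set. Nor are all the reasons treatment failures: refusal and death are not shown to reflect itch response.
- A reader might infer that per-protocol would certainly inflate the benefit. Adverse-event stopping mainly on drug would inflate it, but stopping for insufficient response mainly on placebo can shrink it, as the 5%/15% pattern shows. The protocol gives no split by arm.
- A reader might set 91.7% against the planned 95% and charge about 3 points of power to the all-randomised set. By the same exact method a completers-only analysis has 92.8%, so only about 1 point comes from the analysis set. The rest comes from how the sample size was calculated, which is a separate matter.

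**Conclusion.** The point holds in this form: the protocol states an either/or primary analysis set for a superiority trial and nowhere resolves it. It should be corrected before unblinding, because a choice made afterwards cannot be repaired.

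A free choice takes two-sided type I error to about 6% with equal 10% drop-out and about 8% with 15%/5%. The excess at equal drop-out is modest, about 1 point, but it does not depend on the direction of any bias. A per-protocol primary could also shift the estimated difference by several points either way. In the patterns shown, the shift runs from 9.8 points too high (44.8 v 35.0) to 1.7 points too low (33.3 v 35.0).

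These sizes rest on assumed drop-out by arm, on drop-outs being non-responders, and on the responder endpoint. They do not carry over to the change in WI-NRS that the Summary names as primary.

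**What to change.** 1. **Settle the primary endpoint first.** The Summary (change in WI-NRS) and 5.10 (3-point responder) must agree, because the missing-data rule follows from the endpoint.
2. **Name one primary set in the Summary and in 5.13:** all randomised patients, analysed in the arm to which they were assigned. Define the per-protocol set and label it sensitivity only.
3. **State the missing-data rule.** If the endpoint is responder, count a missing week-6 WI-NRS as non-response. If it is change, state a missing-data method suited to a continuous outcome; counting as non-response does not apply there.
4. **Reduce the missing data.** Obtain the week-6 WI-NRS and Skindex-10 from patients who stop study drug but remain on dialysis, since they can still be asked at a dialysis visit.

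The cost is a few sentences and some continued follow-up. For the responder test, power is about 1 point lower than in a completers-only analysis (91.7% v 92.8%). N stays at 51 per arm for this point.
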